8.9.2 Follicular Engraftment

Multiple samples were obtained at Screening and Visit 5/EOT visits for a subject. The mean of each parameter, Cas5/PanBac, deoR/PanBac, and Transposase2/PanBac ratio, will be determined for each visit and serve as the observation for that visit. The change and percent change in Cas5/PanBac, deoR/PanBac, and Transposase2/PanBac ratio from Screening at Visit 5/EOT will be summarized with descriptive statistics. NB01 and VEH will be compared at Visit 5/EOT using MMRM.

The treatment groups will also be compared with respect to the proportions of subjects with “success” at Visit 5/EOT using the Cochran-Mantel-Haenszel (CMH) test with and without stratification on study center, where “success” is defined as a Follicular Biore® with “yes” outcome based on the recovery of live NB01. If any one of the samples at a given visit has live NB01, the success outcome is “yes” for that visit.

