6. Subject has any skin diseases with compromised skin barrier function (e.g. atopic dermatitis, etc.), such as noticeable breaks or cracks in the skin on the face, including severely excoriated skin or skin with open or weeping wounds suggestive of an active infection or increased susceptibility to infection in the treatment area (i.e., face).
7. Subject has facial hair, scarring or other clinical conditions in the treatment area that could interfere with study assessments, in the opinion of the PI.
8. Subject has active clinically significant periodontal disease in the opinion of the PI, or ongoing procedures (e.g., gum grafting).
9. Subject has history/current ocular infections/surgeries within six months of enrollment, with the exception of any history of cataracts.
10. Subject has a history of septic joints/endocarditis.
11. Subject has sensitivity to or difficulty tolerating any ingredients in the study drug, including glycerin, polyethylene glycol.
12. Subject demonstrates non-compliance with BPO pre-treatment during the Screening period. Non-compliance is defined as BPO application for less than 5 days the week prior to Day 1, failure to apply BPO 24-48 hours prior to Day 1, and BPO application within approximately 24 hours of the Day 1 visit.
13. Subject is currently participating in an investigational drug, device, or biologic study or has used an investigational drug, biologic or device treatment within 30 days prior to first application of the study drug.
14. Subjects with prosthetic heart valves, pacemakers, intravascular catheters, or other foreign or prosthetic devices/implantable devices/hardware.
15. Subject has a history of chronic HIV, HCV, or HBV infections.
16. Subject has a history of malignancy (with the exception of non-melanoma skin cancer).
17. Subject is immunosuppressed (such as resulting from transplantation, immunosuppressive therapy, active HIV infection/ AIDS, neutropenia).
18. Subject had a major surgical procedure, open biopsy, or significant traumatic injury within 14 days of initiating study drug (unless the wound has healed), or anticipation of the need for major surgery during the study.
19. Subject has a medical or psychiatric condition and/or history of drug or alcohol abuse that, in the opinion of the PI, makes the subject inappropriate for study inclusion.
20. Subjects with close contacts (e.g., spouses, children, or members in the same household) that have severe barrier defects or are immunocompromised.

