8.4.3. Exploratory Engraftment Analyses

The engraftment analyses will be conducted on the ITT and PP populations.

Engraftment Assay

For endpoint of Engraftment Assay of Cas5/PanBac, the absolute and percent change from Screening at each follow-up visit, the comparison between NB01 and vehicle-control will be analyzed using ANCOVA model with the dependent variable being absolute or percent change values and the factor treatment and the Screening value as a covariate in the model, with and without LOCF imputation.

For endpoint of Follicular Biore®, the treatment groups will be compared with respect to the proportions of subjects with “success” at Week 12 using the CMH test with and without stratification on study center, where “success” is defined as a Follicular Biore® with “yes” outcome based on the recovery of live NB01.

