3.2 Exploratory Engraftment Endpoints

Skin Engraftment Assay

- Change and percent change from Screening at EOT in Cas 5/PanBac, deoR/PanBac, and Transposase2/PanBac

Follicular Engraftment Assay

- Change and percent change from Screening at EOT in Cas 5/PanBac, deoR/PanBac, and Transposase2/PanBac
- Proportion of subjects with “success” at EOT where “success” is defined as a Follicular Biore sample with evidence of live NB01

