5. DEFINITIONS

- **Study Day:** The study day is the day of study relative to the first dose date and is calculated by follow-up visit date – first dose date + 1. For a subject who was randomized but not treated, the randomization date will be used.

- “Treatment success” for follicular engraftment assay: A post-Screening Follicular Biore sample having evidence of live NB01.

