6.4 Engraftment Samples

Follicular engraftment sampling will be completed via use of Biore® Strips applied across the bridge of the nose extending to either cheek at Visits 1/Screening and Visit 5/EOT. Results will be reported as both a genotype assessment and as absence or presence of live NB01. Skin surface engraftment sampling will be completed via cheek swab at each visit. Three genotypes (deoR, Cas5, Transposase2) will be assessed and reported as the percentage of total bacteria count (PanBac) for both the follicular and skin surface engraftment samples.

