8.7.5 Baseline Clinical Evaluations

Screening and Baseline IGA scores will be tabulated and descriptive statistics will be for the acne lesion counts, QoL domain scores, sebum production, and the skin surface engraftment parameter Cas5/PanBac ratio will be provided by treatment group and overall for the mITT and PP populations. Results of the follicular engraftment sample at Screening will also be presented as the proportion of subjects with live NB01 by treatment group and overall.

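### Follicular engraftment success is not conditioned on the Screening strip, so a subject positive for live NB01 before dosing and still positive at EOT counts as an engraftment

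*SAP*

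**What the plan says.** SAP 8.9.2 says of the follicular strips: "Multiple samples were obtained at Screening and Visit 5/EOT visits for a subject". The rule for the yes/no outcome is "If any one of the samples at a given visit has live NB01, the success outcome is" yes for that visit. The arms are compared on the Visit 5/EOT outcome by CMH test, with and without stratification on study center.

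The other definitions agree. SAP 5 has "A post-Screening Follicular Biore sample having evidence of live NB01". In SAP 3.2, success at EOT "is defined as a Follicular Biore sample with evidence of live NB01". Protocol 8.4.3 refers to a Week 12 "outcome based on the recovery of live NB01", and protocol 3.2.2 and 8.3.2 follow the same line. None sets a condition on the Screening result.

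That result will exist. SAP 6.4 covers the follicular strips at Screening and EOT: "Results will be reported as both a genotype assessment and as absence or presence of live NB01". Schedule footnote n places the Screening samples before BPO pre-treatment. SAP 8.7.5 then plans a descriptive use: "Results of the follicular engraftment sample at Screening will also be presented as the proportion of subjects with live NB01", by arm and overall. SAP 8.11.4.5 uses success, yes or no, as a subgroup factor for IGA, lesion counts and sebum.

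**The concern.** Live NB01 read on a strip taken before BPO and before the first dose cannot have come from this study's drug. If the same subject is positive again at EOT, the plan records an engraftment, including in a vehicle subject who never received NB01. Nothing later in the plan removes such a subject: the CMH strata are study center or none, and neither the per-protocol criteria (SAP 8.2.3) nor the eligibility criteria mention Screening strip status.

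The plan also treats the same strips in two ways. SAP 8.9.2 analyzes their genotype ratios as change from Screening, but the yes/no outcome drops the pre-dose reading.

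At stake are the absolute NB01 success rate, which is a natural proof-of-concept figure, the contrast with vehicle, and the meaning of the engraftment-success subgroup. The rule that any one positive strip suffices makes a background positive more likely as the number of strips rises.

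**Working it through.** The documents give no rate, effect size or power for this endpoint, so there is no planned figure to reproduce. What follows is an illustration.

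**Inputs from the documents.** 36 subjects at 2:1 (protocol 3.3): 36 × 2/3 = 24 NB01 and 36 × 1/3 = 12 vehicle. The test is the unstratified CMH test (SAP 8.9.2).

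**Assumptions.** Two-sided 0.05. f is the share positive at Screening, e the true engraftment rate, and no vehicle subject truly engrafts. Main case, full persistence: every Screening-positive subject is positive again at EOT.

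**Success rates as defined.** NB01 = f + (1 − f)e; vehicle = f; difference = (1 − f)e. For e = 0.40 and f = 0.10: NB01 = 0.10 + 0.90 × 0.40 = 0.46, vehicle = 0.10, difference = 0.36 instead of 0.40.

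**Power.** With a successes among n1 = 24 on NB01, m successes in total and N = 36, the statistic is (a − n1·m/N)² ÷ [n1·n2·m(N − m)/(N²(N − 1))] on 1 df. Power sums the binomial probabilities of all tables with p < 0.05. For the Screening-negative analysis, it is averaged over the random number of subjects excluded from each arm.

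Two cases are compared for that analysis:
- Persistent: after exclusion the rates are e v 0.
- Independent: a Screening positive is a false call unrelated to the one at EOT. The EOT rates stay at f + (1 − f)e v f, and only subjects are lost.

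Results for e = 40%:

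| f | NB01 v vehicle as defined | Difference | Power as planned | Screening-negative, persistent | Screening-negative, independent |
|---|---|---|---|---|---|
| 0 | 40% v 0% | 40 points | 90% | 90% | 90% |
| 5% | 43% v 5% | 38 points | 74% | 87% | 71% |
| 10% | 46% v 10% | 36 points | 62% | 83% | 57% |
| 20% | 52% v 20% | 32 points | 45% | 72% | 37% |

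At e = 50%, planned power is 99%, 90%, 80% and 64% for f = 0, 5%, 10% and 20%. Under persistence, the Screening-negative analysis gives 99%, 98%, 97% and 92%.

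**Mislabeled subjects under full persistence.** Expected background successes are 24f on NB01 and 12f on vehicle: 1.2 and 0.6 at 5%, 2.4 and 1.2 at 10%, 4.8 and 2.4 at 20%. The chance of at least one vehicle success is 1 − (1 − f)^12 = 46%, 72% and 93%.

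**Type I error.** With both arms at rate f, the rejection probability is 0.035 at f = 5%, 0.036 at 10%, 0.038 at 20% and 0.045 at 30%, below 0.05 throughout.

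**The case against.** A reader might infer that every Screening-positive subject is counted as an engraftment. The documents do not support that: a strip at Visit 5/EOT must also be positive. Between the two readings come 5 to 7 days of BPO, meant to lower the resident bacterial load (protocol 1.2.3), and the time to Day 80. Full persistence is an assumption with no source.

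A reader might also infer that Screening positives are common. Protocol 1.1 points the other way, describing the strain as a sequence type without earlier reports. Earlier exposure is possible on paper, since exclusion 13 reaches only a subject who "has used an investigational drug, biologic or device treatment within 30 days prior to first application of the study drug" and an earlier NB01 study treated 10 subjects. But that was a single-dose, single-center study, and nothing says that any of its subjects enrolled here or still carry the strain. The specificity of the live-NB01 reading is not given, so false calls cannot be ruled out, but no text supports f = 5% to 20%.

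Nor does the plan overlook Screening status altogether. SAP 8.7.5 reports it by arm, and the randomized vehicle arm shows background positivity at EOT. Randomization makes the background equal in expectation, so it dilutes the contrast and does not favor NB01.

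The strongest point concerns the remedy. If false calls arise afresh at each visit, dropping Screening positives removes subjects without removing false positives, and power falls slightly (62% to 57% at f = 10%). This stands, and is a reason to show the conversion analysis beside the all-subject result and not in its place. The endpoint is also exploratory, in a study with no sample-size calculation, so no power target is missed.

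**Conclusion.** The point holds as a gap in the definition. As written, follicular success can count carriage that predates dosing, in either arm, and pass it into the engraftment-success subgroup. The consequences are overstated absolute rates and a difference shrunk from e to (1 − f)e under full persistence.

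The size is unknown. If no subject is positive at Screening, nothing changes. At an assumed e = 40% and f = 10% with full persistence, the vehicle rate is 10% where it should be 0, the difference is 36 points where it should be 40, and power is 62% against 83% in the Screening-negative analysis. A claim that the test would falsely declare engraftment is not supported, because type I error stays below 0.05. The gap is worth closing because the data are already collected and a choice made after seeing the Screening table by arm would be post hoc.

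**What to change.** Before unblinding:

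- In SAP 8.9.2, add a conversion analysis: no live NB01 on any Screening strip and live NB01 on at least one strip at Visit 5/EOT, among Screening-negative subjects, by the same CMH test. Show it beside the all-subject result.
- In SAP 8.11.4.5, use conversion status for the engraftment subgroup.
- State how a subject with a missing Screening strip is handled. SAP 8.11.4.1 gives a missing-data rule for IGA success but none for this outcome.
- Read the Screening proportion already planned in SAP 8.7.5, together with the vehicle arm's EOT rate, as the background positive rate.

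The cost is a few lines of SAP text and one more table, with no new sampling. About f × 36 subjects leave the conversion denominator: 1.8 at 5%, 3.6 at 10%, 7.2 at 20%. The rule does not remove false positives that first appear at EOT; the vehicle arm's EOT rate is the guide to those.

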8.10 Exploratory Sebum Evaluation

8.10.1 Sebum Production

For the endpoint of sebum production, the observed, change and percent change from Screening values at each follow-up visit will be summarized with descriptive statistics. NB01 and VEH will be compared at Visit 5/EOT using MMRM.

Sebum production data will not be available for all subjects. One site, [name] (Site 4), did not have a Sebumeter, therefore, sebum production was not assessed for any subject. Site 3, [name], received a Sebumeter after having started enrollment of subjects. Some of the site’s subjects will not have any sebum data while others may have only partial data with the Screening values missing. Subjects without any sebum data will be excluded from the summaries and analyses. Subjects with partial data will be included in the summaries for observed values where data is

available, but will be excluded from summaries and analyses for change and percent change from Screening.

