Follicular engraftment sampling will be completed via use of Biore® Strips applied across the bridge of the nose extending to either cheek. Skin surface engraftment sampling will be completed via cheek swab.

Exploratory
Efficacy:

Investigator's Global Assessment (IGA)

Overall severity of acne will be assessed using a five-point scale where 0=Clear, 1=Almost Clear, 2=Mild, 3=Moderate, and 4=Severe. This is a static morphological scale that refers to a point in time and not a comparison to Baseline (see [Appendix 3](#)).

Acne Lesion Counts

The number of total lesions, inflammatory lesions (papules and pustules), and non-inflammatory lesions (open and closed comedones) on the face (including those present on the nose) will be counted. Counts of nodules and cysts will be reported separately and are not to be included in the inflammatory or non-inflammatory lesion counts.

Acne Quality of Life (QoL) Questionnaire

At each visit, subjects will be asked to complete the Acne QoL Questionnaire to assess subjective improvement of acne (see [Appendix 5](#)).

Exploratory Sebum:

Sebum Production

At each visit, sebum levels will be assessed for any changes from Screening, Baseline to Weeks 2, 7, and 12 at sites 02 and 03. Sebum production data will not be available for all subjects. Site 04 did not have a Sebumeter, therefore, sebum production was not assessed for any subject. Site 03 received a Sebumeter after having started enrollment of subjects. Some of the site's subjects will not have any sebum data while others may have only partial data with the Screening values missing. Subjects without any sebum data will be excluded from the summaries and analyses. Subjects with partial

data will be included in the summaries for observed values where data is available, but will be excluded from summaries and analyses for absolute change and percent change from Screening.

Study Endpoints:

- | | |
|--------------------------|---|
| Primary Safety: | 
• Incidence (severity and causality) of any local and systemic AEs.• Number of subjects with presence (and severity) of each LSR and each time point.• Changes from Screening/Baseline in physical examination findings at Visit 5/EOT.• Changes from Screening/Baseline in vital signs at Visit 5/EOT. Changes from Screening in local CBC at Visit 5/EOT. |

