6.2.2. Baseline Assessments – Visit 2 (Day 1)

The following will be performed and documented at the Day 1 visit:

- Reconfirm inclusion/exclusion criteria and subject eligibility.
- Review of Screening Subject Diary.
- Limited physical examination.
- Vital signs.
- UPT.
- Sebum levels, measured at the mid-glabellar region of the forehead using a Sebumeter SM – 815 (COURAGE + KHAZAKA electronic GmbH, Köln, Germany).
- Assess AEs.
- Assess LSRs.
- Review concomitant medications, topical facial products and procedures/therapies.
- IGA.
- Acne Lesion Counts (total, inflammatory, and non-inflammatory lesion counts).
- Quality of life assessment (Acne QoL Questionnaire).
- Optional facial photography.
- Cheek swab skin engraftment sample.
- Randomize the subject (see [Section 5.1.1](#)).
- PI or designee shall apply the first dose of study drug and review application instructions with the subject.

- Dispense Subject Diary (for documentation of at-home Cetaphil® BID washes and evening study drug application).
- Dispense Study Drug and gloves, reminding the subject that study drug is to be stored in the freezer
- Schedule the next visit.

6.2.3. Treatment Assessments - Visit 3 (Week 2/Day 8), Visit 4 (Week 7/Day 43) and Visit 5 (Week 12/End of Treatment/Day 80)

The following will be performed and documented at each visit during the treatment phase:

- Collect, review, and dispense Subject Diary. NOTE: In review of the Subject Diary, the PI should question the subject to gauge understanding of application instructions, and re-instruct, at each visit except Visit 5, EOS.
- Sebum levels, measured at the mid-glabellar region of the forehead using a Sebumeter SM – 815 (COURAGE + KHAZAKA electronic GmbH, Köln, Germany).
- Assess AEs.
- Assess LSRs.
- Review concomitant medications, topical facial products and procedures/therapies.
- Limited physical examination (**Visit 5/EOT only**).
- Vital signs (**Visit 5/EOT only**).
- UPT (**Visit 5/EOT only**).
- Local CBC (**Visit 5/EOT only**).
- IGA.
- Acne Lesion Counts (total, inflammatory, and non-inflammatory lesion counts).
- Quality of life assessment (Acne QoL Questionnaire).
- Optional facial photography.
- Cheek swab skin engraftment sample.
- Face wash with Cetaphil® (**only at Visit 5/EOT prior to Biore® strip sampling**).
- Biore® strip follicular engraftment sample (**Visit 5/EOT only**).
- Dispense Study Drug (**only at Visit 3 and Visit 4**).
- Schedule the next visit.

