8.9.1 Skin Engraftment

For the endpoint of skin engraftment, the change and percent change in Cas5/PanBac, deoR/PanBac, and Transposase2/PanBac ratio from Screening at each follow-up visit, will be summarized with descriptive statistics at each visit. NB01 and VEH will be compared at Visit 5/EOT with respect to change or percent change values using Mixed effect Model Repeated Measures (MMRM).

The MMRM model used for the analysis of continuous variables will include treatment, visit, treatment by visit, and investigator site as fixed effects, the Screening value as a covariate, and subject as a random effect. The MMRM analyses will be based on observed data. The p-value for the hypothesis of no treatment difference at Visit 5/EOT will be reported. The MMRM analysis will use an unstructured covariance type. The Kenward-Roger method will be used to estimate denominator degrees of freedom.

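### The planned sebum comparison drops Site 03 subjects who lack a Screening reading, so their later readings go unused and some precision is lost

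*SAP*

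**What the plan says.** Protocol section 2 and SAP 3.1 set an exploratory objective of evaluating treatment effects on sebum at sites 02 and 03. Site 04 had no device. According to SAP 8.10.1, Site 03 "received a Sebumeter after having started enrollment of subjects", so some of its subjects have no sebum data and "others may have only partial data with the Screening values missing".

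SAP 8.10.1 keeps the second group in the observed-value summaries "but will be excluded from summaries and analyses for change and percent change from Screening". The protocol synopsis (Exploratory Sebum) has the same rule: "but will be excluded from summaries and analyses for absolute change and percent change from Screening".

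The comparison of arms is at Visit 5/EOT by MMRM. The model is set out in SAP 8.9.1 for continuous variables generally. It has treatment, visit, their interaction and site, with "the Screening value as a covariate, and subject as a random effect", an unstructured covariance, and a p-value as the named output.

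Sebum is scheduled at every clinic visit. The Day 1 list in protocol 6.2.2 includes "Sebum levels, measured at the mid-glabellar region of the forehead", and footnote b of the Schedule of Events places Day 1 procedures before the first application. Footnote i places the Screening procedures before benzoyl peroxide pre-treatment, so that pre-treatment lies between the two readings.

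**The concern.** SAP 8.11.4.1 relies on MMRM to deal with missing data without imputation. That works for missing outcomes but not for a missing covariate, and change from Screening is itself undefined without the Screening value. For sebum the rule therefore amounts to complete-case deletion. Randomised subjects with observed post-dose readings leave the only between-arm comparison because a device was delivered late.

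Only 36 subjects were randomised, one of three sites has no sebum data, and part of another has none. The comparison is small before this rule applies. SAP 8.11.4.5 then divides sebum by sex, age and follicular engraftment success, where each lost subject costs more. The analysed set is also narrower than the sites 02 and 03 subpopulation named in the objective.

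**Working it through.** The documents give no sample size, precision or power figure for sebum, so there is no stated figure to reproduce. The question is how much the standard error (SE) of the Visit 5 difference grows when affected subjects are dropped, all else equal.

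**From the documents:** 36 randomised, 2:1 allocation, two pre-dose visits (Screening, Day 1), three follow-up visits (Weeks 2, 7, 12).

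**Assumed:** 24 subjects with sebum data (16 NB01, 8 vehicle), SD 1, equal correlation ρ = 0.6 between visits, covariance known, no dropout, and common pre-dose means in both arms.

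**Formula.** For a subject with p pre-dose readings, let c = pρ²/(1 + (p − 1)ρ) and λ = (1 − c) + 2(ρ − c). At ρ = 0.6:

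- p = 2: c = 0.72/1.6 = 0.45, λ = 0.55 + 0.30 = 0.85
- p = 1 (Day 1 only): c = 0.36, λ = 0.64 + 0.48 = 1.12
- p = 0 (follow-up only): c = 0, λ = 1 + 1.2 = 2.2

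With n complete subjects and m subjects lacking Screening in an arm, the variance of the adjusted Visit 5 mean is

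V = (1/3)/(n/0.85 + m/λ) + (2/3)(1 − ρ)/(n + m).

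With m = 0 this is 0.55/n. The SE is the square root of the sum over the two arms.

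**Example: 4 lost (3 NB01, 1 vehicle).**

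- Dropped: 0.55/13 + 0.55/7 = 0.0423 + 0.0786 = 0.1209, SE 0.348.
- Kept with Day 1: NB01 (1/3)/(15.294 + 2.679) + 0.2667/16 = 0.0352; vehicle (1/3)/(8.235 + 0.893) + 0.2667/8 = 0.0699; sum 0.1051, SE 0.324.
- Ratio: 0.348/0.324 = 1.07.

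| Lost (NB01 + vehicle) | SE if dropped | Ratio, kept with Day 1 and follow-up | Ratio, kept with follow-up only |
|---|---|---|---|
| 1 (1 + 0) | 0.325 | 1.010 | 1.008 |
| 2 (1 + 1) | 0.340 | 1.050 | 1.039 |
| 4 (3 + 1) | 0.348 | 1.073 | 1.056 |
| 6 (4 + 2) | 0.371 | 1.136 | 1.104 |
| 8 (5 + 3) | 0.400 | 1.217 | 1.165 |

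A full generalised least squares calculation with a site term gives the same ratios to within 0.001.

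**Sensitivity.**

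- *Arm split.* Four lost as 4 + 0 or 2 + 2 gives about 5% or 11%. Eight lost as 6 + 2 or 4 + 4 gives about 17% or 30%.
- *Correlation.* Over 0.3 to 0.7, the figure for 8 lost runs from 23% down to 21% with Day 1, and from 22% down to 15% with follow-up only.
- *Number of subjects.* A cruder version has one pre-dose reading per subject, losses in proportion to allocation, and a t interval on n − 4 degrees of freedom. Over 18 to 30 subjects and 1 to 8 lost, the excess interval width runs from about 1% to 53%.

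**Separating out the gain from Day 1.** Adding Day 1 as a second pre-dose reading for everyone, with nobody lost, already changes the SE by √(0.64/0.55) = 1.08. The table uses both readings for complete subjects on both sides of the ratio, so it measures subject loss alone.

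**The case against.** The rule is prespecified identically in both documents, with its cause. It follows from the endpoint, because change from Screening cannot be formed without Screening. The affected subjects' observed values are still tabulated. The endpoint is exploratory, no sample size basis is claimed, and SAP 8.11.4.4 plans no multiplicity adjustment. All of this stands, and it limits the point to a minor one.

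Four stronger readings are tempting, and the documents do not support them.

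- *The loss is much larger.* Comparing an ANCOVA on Screening after exclusion with a joint model that keeps everyone and uses both pre-dose readings gives simulated SE ratios of 1.15, 1.22, 1.25 and 1.34 for 2, 4, 6 and 8 lost. Those ratios include the gain from giving Day 1 to every subject, so they overstate the effect of the exclusion.
- *Each affected subject has a Day 1 reading.* The SAP says only that some may have partial data. Having Day 1 without Screening requires the device to have arrived between those visits, a gap of at most 14 days in protocol 6.2.1 or 28 in SAP Table 3. Subjects dosed before delivery have follow-up readings only. The number affected could also be zero.
- *The exclusion biases the treatment effect.* The stated cause is device delivery, which gives no reason to expect differential loss between randomised arms.
- *A planned interval becomes wider.* SAP 8.9.1 names only a p-value. The effect is on the standard error behind it.

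The objection about model size also stands. Moving two pre-dose visits into the response raises an unstructured covariance from 3 × 4/2 = 6 to 5 × 6/2 = 15 parameters. In about 24 subjects this may not converge, and estimating the covariance will erode part of the gain computed above with it known.

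**Conclusion.** The point holds as a minor loss of precision. If at least one Site 03 subject has follow-up sebum data but no Screening value, the plan discards usable randomised data from its only sebum comparison. Under the stated assumptions the standard error is about 1% larger for one such subject, 5% for two, 7% for four, 14% for six and 22% for eight. With follow-up readings only, the range is about 1% to 17%. The direction does not depend on the assumed numbers. The size depends on the count affected, their arm split and the site totals, none of which the documents give.

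**What to change.** Add one supplementary analysis to SAP 8.10.1: a repeated-measures model of observed sebum values at sites 02 and 03.

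- Put the available pre-dose readings in the response, with separate Screening and Day 1 means, each common to both arms. Day 1 then does not stand in for Screening, which matters because pre-treatment lies between them.
- Include treatment-by-visit terms after dosing, and site.
- Report the Visit 5 difference with a confidence interval.
- Prespecify a simpler covariance, such as compound symmetry or heterogeneous Toeplitz, for use if the unstructured one does not converge.
- State by site and arm how many subjects have Screening, Day 1 and Visit 5 readings, so that the size of the loss is visible.

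Keep the planned change and percent-change analyses for subjects who have a Screening value.

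The cost is SAP wording and one extra model, with no new data or visits. The downside is up to 15 rather than 6 covariance parameters if unstructured. Percent change from Screening is not recovered for the affected subjects.
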